**Regenerative Potential of Cultured Gingival fibroblast-
Mesenchymal Stem Cells in Treatment of Periodontal
Intrabony Defects (Randomized Clinical and
Biochemical Trial)**

Protocol of thesis

22- 1- 2016

**Submitted by : [name]**

22- 1- 2016

Introduction:

Fibroblasts are biologically dynamic and morphologically heterogeneous and are the most plentiful connective tissue cells, with different structures depending on their location and activity. The main function of fibroblasts is to keep the structural integrity of connective tissues by continuously secreting precursors of the extracellular matrix. Fibroblasts may act as a novel clue for in situ tissue repair and contribute to cellular mechanisms of mesenchymal stem cell-like features under normal or pathological conditions (Haniffa et al 2007).

Nyman et al.,1989. were claimed that GTR procedure aims at the reconstruction of a periodontal ligament (PDL) with proper oriented and organized collagen fibers inserted in newly formed cementum and newly regenerated alveolar bone. Guided tissue membranes are employed in the hope of excluding epithelium and gingival connective tissue from the root surface due to that they interfere with periodontal regeneration and provide mechanical support for clot formation.

Melcher hypothesis were experimentally established and histologically verified by Karen et al. They have shown that periodontal regeneration occurs when gingival epithelial cells or fibroblasts are excluded from the wound space and periodontal ligament cells are allowed to migrate and populate the wound space. On the other side of research, other studies were reported that gingival connective tissue cells may contribute to the regenerative process. (Lallier et al 2005,(Bartold PM and Narayanan AS.2006).

A later study by *Mitrano et al.2010* showed that gingival tissue cells fulfill the minimal criteria proposed by the International Society for Cellular Therapy to be defined as mesenchymal stem cells. Human gingival tissue-derived mesenchymal stem cells GMSCs are easy to isolate and proliferate faster than BMSCs without any use of growth factors. They have a constant morphology , they maintain a normal karyotype and telomerase activity in long-term cultures and are not tumorigenic(Tomar et al.,2010,Tang et al., 2011) . GMSCs exhibit

strong suppressive effects on the proliferation and activation of human peripheral blood mononuclear cells (PBMC)(Zhang et al., 2009)

MSC are currently defined as plastic adherent, multipotential fibroblast-like cells expressing CD73, CD105 and negative for the hematopoietic markers CD14, CD34 and CD45(Dominici M et al., 2006) but that properties and markers are also shared by fibroblasts. Osteoblastic, chondrogenic, adipogenic differentiation from fibroblasts has also been described (Haniffa MA et al., 2000). Fibroblasts have also the immunosuppressive properties. In fact, it had been comprehensively demonstrated that fibroblasts from various tissue sites inhibit mitogen and allo-antigen stimulated T-cell proliferation (Sarkhosh et al., 2003) and IFN γ production in exactly the same vein as more recent reports using MSC (Klyushnenkova EN et al., 1998).

A novel perforated collagen membrane as a sensory system that could enable participation of gingival fibroblasts and gingival stem cells in GTR procedures (Gamal et al., 2013). That approved in a clinical study that the utilization of a perforated membrane (PM) improved clinical outcomes significantly more than those observed with the use of occlusive membranes. It has likewise been suggested that growth and differentiation factors from cells in the gingival connective tissue could pass through the membrane perforations and augment regeneration. Gamal et al. reported that PM use was associated with significantly higher GCF levels of BMP-2, PDGF-BB and VEGF compared to occlusive membrane (OM) treated sites. They hypothesized that; blood clot occluded membrane perforations could allow for more physiologic growth factor release compared to occlusive membranes (Gamal et al., 2014,2015)

Since cellular responses mainly dependent on specific interactions with extracellular matrix components(ECM), growth factors, or cell surface receptors, ECM act as a constitutive part of stem cell niche, ECM components are key players of the niche instructive power(R. Peerani, P.W. Zandstra.2010) These extracellular macromolecules, by their assembly and three-dimensional arrangement, supply a microenvironment in which the signals deriving from cell-ECM interaction, as well as soluble and ECM-bound factors, are integrated

in a functional manner to allow the maintenance of stem cell homeostasis (M.F. Pera, P.P.L. Tam, 2010).

We hypothesized that if the gingival fibroblasts translocated away from its extracellular matrix components into the periodontal defect to be subject to its same mechanical and biologic media, it could behave the same way as the MSCs. This experimental study was performed in order to evaluate clinically and radiographically regenerative potentials of cultured GMSCs and gingival fibroblasts into intrabony periodontal defects in human.

Aim of the study:

Primary outcome:

Clinical and radiographic evaluation of the regenerative potentials of cultured gingival fibroblasts and GMSCs carried by tri calcium phosphate into intrabony periodontal defects in human.

Secondary outcome:

Biochemical analysis during the healing of intrabony periodontal defect .

Subject and methods:

Twenty patients diagnosed as a moderate to severe chronic periodontitis will be participate in this study, they will be selected from the outpatient clinic, Department of Oral Medicine and Periodontology, Ain Shams University.

All patients will be fully informed about the aim and purpose of this study. An informed consent will be signed by each patient.

I-Patient Selection:**A) Inclusion Criteria:**

Patients were selected according to these criteria.

- 1- Age range from 25 to 50 years.
- 2- Presence of at least two bilateral interproximal osseous defects estimated from radiographic evaluation and transgingival bone sounding ≥ 3 mm of two or three osseous walls.
- 3- Probing Depth ≥ 5 mm after initial therapy.
- 4- Attachment loss ≥ 5 mm.
- 5- Thick gingival biotype more than 1 mm with enough width of attached gingiva.

B) Exclusion Criteria:

- 1- Patients with systemic disease or compromised immune illness regarding Cornell medical index.
- 2- Smoker's patients.
- 3- Pregnant and lactating females.
- 4- Patients with regular use of medications that could compromise wound healing.
- 5- Uncooperative patients (low compliance).

II-Patients grouping:

Group 1:

Ten periodontal defects will receive tri calcium phosphate alone.

Group 2:

The other ten periodontal defects will receive gingival MSCs - fibroblast culture in tri calcium phosphate as a scaffold.

III- Clinical and Radiographic Assessments:

For the selected sites, the following clinical parameters will be assessed preoperative (baseline), 3, and 6 months after the surgical procedure using the same William's graduated periodontal probe.

- 1- Plaque index (PI) *Löe 1967.*
- 2- Gingival sulcus bleeding index (SBI) *Muhlemann, 1963.*
- 3- Probing depth (PD) *Glavind and Loe, 1967.*
- 4- Clinical attachment level (CAL) *Glavind and Loe, 1967.*
- 5- Gingival recession: considered the distance of the gingival margin from the cemento-enamel junction if there were recession preoperative, while if there is no recession the gingival margin above the cemento-enamel junction is considered preoperatively and postoperatively.

Radiographic assessment:

- 1- Assessed at baseline, 3, 6 and 9 months postoperatively using indirect digital radiography (Digora)♦.
- 2- Each radiograph was standardized using a paralleling device with an acrylic bite block that was fixed by the opposite arch by the indentations of the opposing teeth.

♦ Digora Soredex USA www.soredex.com

The radiographic parameters were measured on 2.7 version of Digora software:

- 1- Intrabony defect height.
- 2- Defect surface area.
- 3- Bone density

IV- the gingival crevicular PDGF-BB levels at 1,3, 7, 14,and 21 day:

The measurement of platelet derived growth factor level in the gingival crevicular fluid at different interval will detect the regenerative process in periodontal defect.

V-Surgical protocol:

A) Surgical procedures:

- gingival biopsy will be taken from retromolar area , the tissue will be kept in a-MEM medium in sterile container. And so it will be cultured for 14 days in biochemical department in Cairo University.
- Biopsy medium is consists of Dulbecco's modified Eagle's medium (DMEM) plus penicillin and streptomycin.
- The samples will be cut into small pieces displaced on glass slides and placed in culture plate with basic medium (DMEM+ fetal bovine serum + penicillin and streptomycin)(*Alireza M et al., 2014*).
- It will be maintained in an incubator at 37°C and humidified air (5% CO₂, 95% air). From days 14 to 21, gingival fibroblast cell cultures will reach 80% confluence; the cells will be transferred to tissue culture flasks using a solution of trypsin and EDTA.
- After centrifugation, cells will be resuspended with serum supplemented medium and incubated in 50 cm²culture flask (Falcon).
- After that the minimally invasive technique will be made at the site of the defect and the graft material will be applied.

-All patients will take antibiotics for 1 week (3 · 500mg amoxicillin*/day), (3.250mg metronidazole**/ day) and an anti-inflammatory (3.alphintern***/ day).

-Patients will instruct to rinse twice daily with a 0.12% chlorhexidine digluconate[▫] mouth rinse and to avoid mechanical plaque removal at the site of surgery for 15 to 30 days.-Periodontal dressing was removed after 1 week.

-Sutures will removed 10 day following surgery.

-Patients will instruct not to brush for 2 weeks and not to floss the surgical area for 4 weeks.

- After 15 days patient were instructed to use Bass technique for tooth brushing.

VI-Postoperative surgical evaluation and assessment:

- Weekly recall appointments will schedule during the first 6 weeks after surgery and once per month.
- The follow up period included general and oral examination, plaque and calculus removal when necessary, at the surgical site careful subgingival debridement will carry out with hand instruments.
- Both clinical and radiographic parameters will be recorded at 3and 6 months postoperative.

*The following rule in the unit of Biochemistry and Molecular Biology will be applied to maintain cells culture:

- ✓ Hood preparation
- ✓ Sterile handling .All biological contaminated tissue culture plates, flask, and other non sharps will be placed in non – sharp biohazard waste container. However, an effort to minimize entry /exit from the hood will be made to minimize disturbances in laminar flow at the entrance, which may create the potential to waft in contaminants. Removal of all these biohazards will be under supervision of researcher.
- ✓ Cleaning up

* Amoxil MUP Egypt
 ** Flagyl Sanofi Aventis Egypt
 *** Alphintern Amoun Egypt
 ▫Antiseptol Kahira Pharm Egypt

- ✓ Cell feeding , To enable cells to grow and divide in dish, they will be fed by the nutrients provided by the media. Old media will be replaced with fresh media every two or three days for most animal cell lines
- ✓ Cell splitting ,Cell growing in dish begin to get crowded and then stop growing. This crowded state is called (confluence) and to maintain cells growth, confluent cultures will be split and reseeded into new culture dishes at a lower density.

VII- Statistical analysis:

- All data will be subjected to statistical analysis.
- Description of quantitative variable will be in the form of mean and standard deviation (SD).
- Qualitative variable will be described as number and percentage.
- Comparison between quantitative variable will be carried out using student -t test when normally distributed, and Mannwhitney test for abnormal distribution.

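### Do twenty patients with at least two bilateral defects each conflict with groups of ten and ten defects, and does the unstated unit of randomisation undermine the tests?

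*Protocol*

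**What the plan says.** Under Subject and methods the protocol states: "Twenty patients diagnosed as a moderate to severe chronic periodontitis will be participate in this study". Inclusion criterion 2 in section I requires "Presence of at least two bilateral interproximal osseous defects estimated from radiographic evaluation".

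The next section is headed "II-Patients grouping", but the lines under it count defects. For Group 1: "Ten periodontal defects will receive tri calcium phosphate alone". For Group 2: "The other ten periodontal defects will receive gingival MSCs - fibroblast culture in tri calcium phosphate as a scaffold".

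Section III sets the measurements: "For the selected sites, the following clinical parameters will be assessed preoperative (baseline), 3, and 6 months after the surgical procedure". Section V describes a gingival biopsy and culture ("From days 14 to 21, gingival fibroblast cell cultures will reach 80% confluence") and then surgery: "After that the minimally invasive technique will be made at the site of the defect and the graft material will be applied".

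Section VII names Student's t test, or Mann-Whitney for non-normal data, with significance at P below 0.05. Randomisation is mentioned only in the title. No section says whether patients or defects are randomised, how many defects per patient are treated, or how the study site is picked. Only the protocol was available; a separate SAP may exist.

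**The concern.** Three things pull in different directions. The bilateral criterion is what one would write for a split-mouth trial. The heading groups patients. The lines beneath it group defects, and their total is half the minimum number of eligible defects.

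Two consequences could follow. First, if each patient supplies one defect to each arm, the data are paired. An independent-samples test is then the wrong one, and either the patient count or the defect count is wrong. Second, if each patient supplies one defect out of two or more, someone has to choose it. Culture takes two to three weeks before surgery. If only Group 2 patients were biopsied, the arm would be known for at least 14 days while the choice was still open. Taking the more promising defect in one arm only would bias the difference between groups.

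**Working it through.** **Counts.** Inputs from Subject and methods and sections I and II: 20 patients, at least 2 eligible defects each, groups of 10 and 10.

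- Eligible defects: 20 × 2 = 40 or more.
- Treated defects: 10 + 10 = 20.
- Treated per patient: 20 / 20 = 1.

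The 40 and the 20 measure different things, namely defects that must be present and defects that receive a graft. Three layouts can be set against the text:

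| Layout | Twenty patients | 10 + 10 defects | Bilateral criterion | Unpaired tests |
|---|---|---|---|---|
| Parallel, one defect per patient | fits | fits | met, not needed | fit |
| Split-mouth, 20 / 2 = 10 patients | does not fit | fits | fits | do not fit |
| Split-mouth, 20 patients, 40 defects | fits | does not fit | fits | do not fit |

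Only the first contradicts no stated number. Section V also refers to a single defect site, and Mann-Whitney is an independent-samples test.

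**Parallel layout.** The protocol gives no effect size, SD or power, so there is no sample-size figure to reproduce. With 10 v 10 independent defects, the two-sample t test has 18 degrees of freedom and a type I error of 5.0%. For an assumed difference of 1 SD the noncentrality is 1 × √(10/2) = 2.24, and power is 56%.

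**Choice of defect.** Assume two eligible defects per patient with within-patient correlation r, and a baseline impression that correlates rho with outcome. The better-looking of the two then has an expected outcome higher by rho × √((1 − r)/π) SD.

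- *Chosen in one arm only, after allocation.* At r = 0.5, √(0.5/π) = 0.40. For rho = 0.3, 0.5 and 1.0 the bias is 0.12, 0.20 and 0.40 SD, with simulated type I error 5.7%, 7.2% and 14.1%. Over r = 0.2 to 0.7 and rho = 0.3 to 1.0 the error runs from 5.5% to about 21%. The top of that range needs rho = 1.0, an upper bound, with r = 0.2. At rho = 0.3 it is 5.5% to 6.2%.
- *Chosen by the same rule in both arms, even after allocation.* The gain is equal in both arms and cancels. The simulated type I error is 4.9% to 5.1% over the same range, with bias about zero.

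**If the trial were split-mouth after all.** The mean difference has variance 2(1 − r)/n, but the unpaired test assumes 2/n, so it is conservative. With 10 pairs its type I error is 5.0%, 2.2%, 0.9% and 0.2% at r = 0, 0.3, 0.5 and 0.7. The cost is power. At r = 0.5 and a 1 SD difference, power is about 58% unpaired against 80% paired with 10 pairs, and 94% against 99% with 20 pairs.

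**If 20 defects in 10 patients were randomised individually, 10 to each group.** The unpaired t test keeps a type I error of 4.9% to 5.1% for r = 0.2 to 0.7.

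The correlations and the 1 SD effect are assumptions throughout; the protocol gives neither.

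**The case for a change.** The strongest case for a change is that the unit of randomisation and the choice of study site belong to the design. They govern enrolment and surgery, so an SAP written later could not repair a site chosen with knowledge of the arm. Two investigators could read this protocol and run different trials, and a sentence or two settling it would cost nothing.

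Much of that stands. The ambiguity is real, and the parallel reading leaves the bilateral criterion without an evident purpose. But a protocol may require more extensive disease than it treats; that is a preference about eligibility, not a statistical error.

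The bias argument needs several conditions at once: biopsy limited to Group 2, the defect still open after allocation, a choice that favours one arm, and an impression that predicts outcome. The protocol states none of the first three. It lists the biopsy in the general surgical procedure without limiting it to one group. It has the selected sites measured at baseline, before surgery, with standardised baseline radiographs. That does not prove the site is named before allocation, but it narrows the room for a late choice.

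**Conclusion.** No change is called for. Under the reading that fits every stated number (twenty patients, one treated defect each, 10 v 10), nothing stated gives a wrong result and the named tests hold their 5% level. What remains is missing detail: the unit of randomisation, the treated defects per patient, and the rule for the study site. The counts and the tests point an analyst to a sensible answer.

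The only harmful route is an arm-dependent choice of defect after allocation. It would add 0.12 to 0.40 SD of bias at r = 0.5, but it is a hypothetical that the text does not describe. If the intended design were split-mouth, a stated count would be wrong and a paired test would gain power, though the unpaired test would not produce excess false positives. The conclusion rests on the parallel reading, two-sided testing at 5%, normal data in the simulations, and the assumed correlations given above.

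### Gingival recession is recorded on two oppositely directed scales chosen by preoperative status, so pooled values can cancel and new recession has no defined value

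*Protocol*

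**What the plan says.** Protocol section III (Clinical and Radiographic Assessments), item 5, holds the only definition of recession. For a site that already has recession, the measure is "considered the distance of the gingival margin from the cemento-enamel junction if there were recession preoperative". For a site that has none, "if there is no recession the gingival margin above the cemento-enamel junction is considered preoperatively and postoperatively". Section III fixes the visits: "the following clinical parameters will be assessed preoperative (baseline), 3, and 6 months after the surgical procedure".

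The inclusion criteria in section I require a probing depth of at least 5 mm and "Attachment loss ≥ 5 mm". Neither restricts where the gingival margin lies. Section II sets two groups of ten defects; the first reads "Ten periodontal defects will receive tri calcium phosphate alone".

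Section VII covers all quantitative variables together. They are summarised by mean and SD, and "Comparison between quantitative variable will be carried out using student -t test when normally distributed", with the Mann-Whitney test otherwise. Nothing in it is specific to recession or to preoperative recession status.

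**The concern.** The two measures run in opposite directions. When the margin moves apically, the distance from the junction grows at a site with recession, while the height above the junction shrinks at a site without it. Nothing in the text puts them on one axis.

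The second measure also stays in force after surgery. A margin that starts above the junction and ends below it therefore has no stated value, yet this is newly developed recession, which the parameter ought to capture.

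Item 5 itself provides for both kinds of site, and both can meet the entry criteria. If their values are pooled under section VII, real recession can cancel within a group. A chance imbalance in preoperative status between the groups can also appear as a treatment difference.

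**Working it through.** The protocol states no recession effect, SD or sample-size figure, so there is nothing to reproduce. The only input taken from it is ten defects per group (section II). All millimetre values and shares below are assumptions chosen to show the mechanism.

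**Two single sites, same true shift of 1 mm apically, unsigned distances**
- From 2 to 3 mm below the junction: recorded change 3 - 2 = +1 mm.
- From 2 to 1 mm above the junction: recorded change 1 - 2 = -1 mm.

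**Group mean, unsigned distances**

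Let f be the share of defects without baseline recession and h their starting height above the junction. Every defect shifts 1 mm apically. Sites with recession record +1; sites without it record |h - 1| - h.

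Mean recorded change = (1 - f) + f(|h - 1| - h)

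This equals 1 - 2f when h is at least 1 mm, and 1 - 2hf when h is below 1 mm. The false gap between two groups is 2 × min(h, 1) × |f1 - f2|.

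| h | f = 0.3 | f = 0.6 | False gap | Signed distance, both groups |
|---|---|---|---|---|
| at least 1 mm | 1 - 0.6 = +0.4 | 1 - 1.2 = -0.2 | 0.6 mm | +1.0 |
| 0.5 mm | 1 - 0.3 = +0.7 | 1 - 0.6 = +0.4 | 0.3 mm | +1.0 |
| 0 mm | +1.0 | +1.0 | 0 | +1.0 |

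Cancellation is complete (mean 0) only when f = 0.5 and h is at least 1 mm.

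**Height allowed to go negative**

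If the second measure is a height that becomes negative below the junction, each such site records -1 whatever h is. The mean is then (1 - f) - f = 1 - 2f for every h, so the figures in the first row apply throughout.

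**Values at a visit instead of change**

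Unsigned, a margin 1 mm above the junction and a margin 1 mm below it both score 1 mm. Comparing raw follow-up values therefore does not avoid the problem.

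**Margin crossing the junction, from 0.5 mm above to 0.5 mm below**
- Unsigned distance: |0.5 - 1| - 0.5 = 0 mm.
- Height floored at zero: max(0.5 - 1, 0) - 0.5 = -0.5 mm.
- Signed distance, apical positive: 0.5 - (-0.5) = +1 mm.

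**How often groups of ten would be unbalanced**

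Let X and Y be the numbers without baseline recession in each group, taken as independent Binomial(10, p). The difference used above, 0.6 against 0.3, is 3 defects in 10. P(|X - Y| ≥ 3) is:
- 0.263 at p = 0.5 (equal to 2 × P(Bin(20, 0.5) ≤ 7) = 2 × 0.1316);
- 0.220 at p = 0.3 or 0.7;
- 0.060 at p = 0.1 or 0.9.

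**The case against.** The strongest reply is that the harm depends on readings the protocol does not state. It never says that values are unsigned. Item 5 shows which side of the junction the margin is on at baseline, so a sign could be assigned to that reading without new data. Pooling is inferred from a generic rule, and section VII does not name change from baseline as the quantity compared. Sign coding is also the kind of detail often left to an analysis plan or data dictionary. The share of sites without recession is unknown; if nearly all sites are of one kind, the effect is negligible. The imbalance probabilities assume independent defects, whereas the inclusion criteria ask for bilateral defects. If a patient contributed one defect to each group, status would probably be correlated and imbalance less likely. Finally, if attachment level is referenced to the cemento-enamel junction (the protocol does not define it), attachment level minus probing depth gives the signed margin position at each visit.

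Much of this stands as a limit on size: the magnitude is not established for this trial. It does not remove the defect. Item 5 is not silent; it fixes a status-dependent rule for what is recorded. Baseline side does not tell the side at follow-up for a margin that crosses, and if direction is not recorded then, later coding cannot reliably recover it. A signed height still runs opposite to the recession distance and must be aligned before pooling. The route through attachment level rests on an undefined reference point, and the protocol does not propose it.

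**Conclusion.** The concern holds. Followed literally, item 5 gives a recession mean that cannot be interpreted when both kinds of site are present, and no defined value for recession that first appears after surgery. The illustrative false gap runs from 0 to 0.6 mm for a true uniform shift of 1 mm. That range assumes unsigned scoring, pooling, and shares of 0.3 and 0.6 without baseline recession; the actual shares and starting heights are not given. The consequence is confined to recession, one of five listed clinical parameters and not singled out as primary. Probing depth and attachment level are listed separately. It should be corrected, but it does not by itself undermine the trial's main comparison.

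**What to change.** Replace the two-part definition in section III, item 5 with one measure for every defect and visit: the signed distance from the cemento-enamel junction to the gingival margin, apical positive and coronal negative, whatever the preoperative status. State that its change from baseline is what is analysed. Margins that cross the junction then have a value, and equal shifts count equally in both groups.

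The cost is one sentence. The same probe reading is used, so no measurement is added.

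### Section VII compares quantitative outcomes without adjusting for the baselines the trial already plans to collect: a loss of precision, not an error, and cheap to recover

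*Protocol*

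**What the plan says.** Section VII of the protocol gives one rule for all quantitative variables: "Comparison between quantitative variable will be carried out using student -t test when normally distributed, and Mannwhitney test for abnormal distribution". Neither that section nor any other names a baseline covariate. Section VII also does not say whether the test is applied to follow-up values or to change from baseline.

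Baselines are planned. For the clinical measures, section III says "the following clinical parameters will be assessed preoperative (baseline), 3, and 6 months after the surgical procedure" and lists five: plaque index, sulcus bleeding index, probing depth, attachment level and recession. For the radiographs it says "Assessed at baseline, 3, 6 and 9 months postoperatively using indirect digital radiography" and lists three: defect height, defect area and bone density. Leaving out the two index scores, six of the eight are continuous. Clinical and radiographic evaluation is the stated primary outcome. Growth factor in crevicular fluid is first sampled on day 1, so it has no listed baseline and is outside this point.

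Two other passages bear on the size of the effect:

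- The entry criteria set floors at baseline: "Probing Depth ≥ 5 mm after initial therapy" and "Attachment loss ≥ 5 mm".
- The design can be read in two ways. The protocol says "Twenty patients diagnosed as a moderate to severe chronic periodontitis will be participate in this study", and for the control group "Ten periodontal defects will receive tri calcium phosphate alone", with ten more defects in the cell group. Twenty defects in twenty patients fits one defect each. Yet inclusion criterion 2 requires "Presence of at least two bilateral interproximal osseous defects", which leaves pairing within patients open.

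**The concern.** With ten defects per group, the groups can easily differ at baseline by chance. An unadjusted comparison carries part of that difference into the treatment estimate. It also leaves in the residual the variation that the baseline could explain.

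How much this costs depends on the correlation between baseline and follow-up and on the ratio of their SDs. The protocol gives neither. Whoever analyses the data must therefore choose between follow-up values and change without knowing which is the poor choice here, and the poor choice can be costly. Adjusting for baseline stays close to the better of the two in either case, and uses data already planned.

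**Working it through.** The protocol states no effect size, SD, correlation or power, so there is no figure of its own to reproduce.

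**Inputs.** From the protocol: 10 defects per group and a 5% level (two-sided assumed). Assumed, with ranges: r, the baseline to follow-up correlation; k = baseline SD / follow-up SD; a true effect of 1 follow-up SD; normal data; independent defects.

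**Formulas** (noncentral t, variances in follow-up SD units):

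- Follow-up values: variance 2/10 = 0.2, noncentrality 1/√0.2 = 2.236, 18 df.
- Change: variance (1 + k² − 2rk) × 0.2, 18 df.
- ANCOVA: variance (1 − r²) × 0.2 × (1 + F(1,18)/18), 17 df, averaged over chance baseline imbalance. The last factor has mean 17/16. The result does not depend on k.

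**Power (%), normal data**

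| r | Follow-up | Change, k = 1 | Change, k = 0.8 | Change, k = 0.6 | ANCOVA |
|---|---|---|---|---|---|
| 0 | 56 | 32 | 38 | 44 | 54 |
| 0.3 | 56 | 43 | 50 | 56 | 58 |
| 0.5 | 56 | 56 | 64 | 68 | 66 |
| 0.7 | 56 | 78 | 83 | 83 | 82 |

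**Break-even.** ANCOVA has the smaller variance than follow-up values when (1 − r²) × 17/16 < 1, so r² > 1/17 and r > 0.24. Change does best relative to ANCOVA when k = r, since 1 + k² − 2rk then equals 1 − r². ANCOVA loses there only through the imbalance factor and the lost degree of freedom.

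**Worst shortfall from the best of the three** (r from 0 to 0.8, k = 0.6, 0.8, 1 and 1.25):

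- ANCOVA: 2.7 points (72.6 against 75.3% at k = r = 0.6)
- Follow-up values: 38 points (56 against 94% at k = r = 0.8)
- Change: 30 points (26 against 56% at k = 1.25, r = 0)

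**Chance imbalance.** The baseline difference D has SD √0.2 = 0.447 baseline SD, so the chance that it exceeds 0.5 SD in either direction is 26%. With b = r/k, it moves the estimate by bD for follow-up values and (b − 1)D for change. At r = 0.7 and D = 0.5 baseline SD, the shifts are +0.35 and −0.15 follow-up SD for k = 1, and +0.35 and +0.05 for k = 0.6. The shifts are opposite in sign only when b is below 1, and the entry floors may make k small enough for b to exceed 1.

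**Skewed data**, where the protocol would use Mann-Whitney (simulated lognormal follow-up values, additive shift, 10 per group):

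| Case | r | Mann-Whitney | Raw-scale ANCOVA |
|---|---|---|---|
| log SD 1, shift 1 SD | 0 | 89 | 71 |
| | 0.5 | 89 | 78 |
| log SD 0.5, shift 1 SD | 0 | 67.5 | 60 |
| | 0.5 | 66 | 69 |

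At log SD 0.8 with a shift of 0.8 SD and r = 0, 0.3, 0.5 and 0.7, ANCOVA on ranks gives 70, 73, 77 and 87% and on logs 73, 77, 82 and 92%. Mann-Whitney gives 68 to 70%. Type I error for the rank and log versions was 4.6 to 5.2%.

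**Ten pairs** (between-defect correlation of 0.3 assumed; 9 df, or 8 if adjusted). At k = 1, power is 66% for follow-up values; 39, 52, 66 and 87% for change; and 60, 64, 72 and 87% adjusted. The worst shortfalls are 31, 34 and 6.1 points. Adjustment beats both others only for r from 0.37 to 0.70 at k = 1, from 0.37 to 0.44 at k = 0.8, and above about 0.85 at k = 0.6.

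**The case against.** The strongest reply is that nothing here is wrong. The t and Mann-Whitney tests are valid for independent randomised defects, and covariates are often left to an analysis plan. The first half stands: a reader might infer an inflated false-positive rate, and neither the protocol nor the calculations support that (simulated type I error for the t test was 4.9 to 5.1%). The second half carries less weight, because section VII does not leave the method open. It names one.

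A reader might also infer that the plan ignores the baseline altogether. The text does not establish this. A test on change would use it, and change narrowly beats ANCOVA in some settings (83 against 82% at k = 0.8, r = 0.7; 68 against 66% at k = 0.6, r = 0.5). The entry floors make a smaller baseline SD plausible, so this objection stands as a limit on the gain.

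The most damaging objection concerns skew. It is tempting to say that ANCOVA never costs more than about 3 points. That is untrue of raw values in the branch where the protocol prescribes Mann-Whitney, so the remedy must include a rank or log scale.

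Finally, all magnitudes rest on assumed values, and the pairing question is unresolved. Both stand. The protocol does not show that the design is paired, so it would be too much to say that the two-sample test is the wrong model.

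**Conclusion.** The point holds as an efficiency improvement. Section VII fixes an unadjusted method for outcomes that include the primary ones, while baselines for those outcomes are already planned.

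For independent defects and normal data, against follow-up values, ANCOVA gains about 10 power points at r = 0.5 and 26 at r = 0.7, and loses up to 2.7 when r is below about 0.25. Against change at equal SDs it gains about 22 points at r = 0, 10 at r = 0.5 and 4 at r = 0.7. That gain shrinks or slightly reverses when the baseline SD is the smaller one. With skewed data the advantage survives only on a suitable scale: rank ANCOVA is about equal to Mann-Whitney at r = 0 and better above it. If the defects are pairs, the case is weaker.

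The correlation, SD ratio, effect size, shape of the data and between-defect correlation are all assumptions. What does not depend on guessing them well, for independent defects, is that adjustment on a suitable scale has a small worst case while either unadjusted choice can have a large one.

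**What to change.** In section VII:

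1. State whether the twenty defects are independent or within-patient pairs.
2. If independent, make the main comparison of each quantitative measure with a baseline an ANCOVA of the follow-up value on group and the baseline of the same measure. Use ranks or a log scale where the protocol would have used Mann-Whitney. If the plaque and bleeding indices are analysed as quantitative, they follow the same rule.
3. If paired, regress the within-patient difference in change on the within-patient baseline difference, and take the intercept as the treatment effect.
4. Keep the t or Mann-Whitney test as a secondary analysis.

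The cost is a few sentences and no new data. One residual degree of freedom is spent: 17 instead of 18 if independent, 8 instead of 9 for ten pairs. The power given up is at most about 3 points if independent with normal data, and about 6 if paired. A rank analysis gives no effect in millimetres, so report the group means and SDs alongside it.
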